8. In women with the potential for pregnancy (including patients with amenorrhea due to medical reasons, such as chemical menopause), after consenting to the study, the patient must agree to take contraception from enrollment and for at least 23 weeks after taking the final dose of the investigational drug (a period of 30 days [ovulation cycle] is added to five times the elimination half-time of I/O agent). Women with the potential for pregnancy include those who have begun menstruation, who have not undergone a hysterectomy, bilateral tubal ligation, or bilateral oophorectomy, and who have not gone through menopause. Menopause is defined as the consecutive absence of menstrual periods for ≥ 12 months. Total abstinence is an acceptable mode of contraception.
9. In the case of men, the patient must agree after consenting to the study to take contraception from enrollment and for at least 31 weeks after taking the final dose of the investigational drug (a period of 90 days [the spermatogenesis cycle] is added to five times the elimination half-time of I/O agent. Total abstinence is an acceptable mode of contraception.

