7.3.1.1.7 Outcome

The outcome of the AE is to be documented as follows:

- Recovered/resolved
- Recovering/resolving
- Recovered/resolved with sequelae
- Not recovered/not resolved
- Fatal
- Unknown

Assessments and documentation of adverse events

The definition of adverse events (AEs) is given on Section 7.3.1.1.

All AEs, SAEs and other reportable safety events that occur after the consent form is signed but before treatment allocation/randomization must be reported by the investigator.

- All AEs from the time of treatment allocation/randomization through 30 days following cessation of study treatment must be reported by the investigator.
- All AEs meeting serious criteria, from the time of treatment allocation/randomization through 30 days following cessation of study treatment if the participant initiates new anticancer therapy, whichever is earlier must be reported by the investigator.
- All pregnancies and exposure during breastfeeding, from the time of treatment allocation/randomization through 120 days following cessation of study treatment, or 30 days following cessation of study treatment if the participant initiates new anticancer therapy must be reported by the investigator.
- Additionally, any SAE brought to the attention of an investigator at any time outside of the time period specified above must be reported immediately by the investigator if the event is considered to be drug-related.

Investigators are not obligated to actively seek AE or SAE or other reportable safety events in former study participants. However, if the investigator learns of any SAE, including a death, at any time after a participant has been discharged from the study, and he/she considers the event to be reasonably related to the study treatment or study participation, the investigator must promptly notify Merck.

Reporting of serious adverse events

The definition of serious adverse events (SAEs) is given on Page Section 7.3.1.2.

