Each serious adverse event must be followed up until resolution or stabilization, by submission of updated reports to the designated person. An isolated laboratory abnormality that is assigned grade 4, according to CTC definition, is not reportable as an SAE; unless the investigator assesses that the event meets standard ICH criteria for an SAE. CTC grade 4 baseline laboratory abnormalities that are part of the disease profile should not be reported as an SAE, specifically when they are allowed or not excluded by the protocol inclusion/exclusion criteria.

Throughout the course of the STUDY, the Principal Investigator and study personnel agree to comply with the obligations of adverse event reporting as set forth below, 'Safety Reporting Requirements' and with FDA regulations.

SPONSOR/ INSTITUTION is responsible for all the pharmacovigilance obligations and safety reporting pursuant to the applicable law and regulations in the country where the STUDY is performed.

Additionally, the SPONSOR/INSTITUTION shall immediately, within 24 hours at the latest, report to BAYER by fax or and/or email and to Merck. Merck Global Safety. (Attn: Worldwide Product Safety; [contact]).

(1) any other relevant safety information including but not limited to:

- a. reports of drug exposure via mother / father with and without adverse events (exposure during conception, pregnancy, childbirth and breastfeeding) including their outcome;
- b. if linked to a serious adverse event, reports of misuse, abuse, overdose , medication error and other uses outside what is foreseen in the protocol, drug dependency, occupational exposure, suspected transmission of an infectious agent, withdrawal syndrome, drug interactions with respect to the STUDY DRUG;

and

(2) any communication concerning safety related information to regulatory authorities or ethics committees including but not limited to:

- Development Safety Update Reports / relevant parts of IND reports for the STUDY;
- Any other safety related reports, issues and queries that are either raised by or communicated to regulatory authorities or ethics committees (e.g. reportable non-serious cases);

CONTRACT PARTNERS commit to promptly respond to any query from BAYER and Merck regarding adverse event documentation. This will include queries related to specific treatment assignment for reported Serious Unexpected Adverse Drug Reactions.

Safety Reporting Requirements

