The Investigator/ Sponsor shall report to USC, Bayer and Merck within 24 hours of the investigator's awareness of other events such as:

- An adverse event related to study specific procedures
- Any new and important event related to treatment with the study drug(s).
- Any pregnancy during which a female patient was exposed to the study drug(s)
- Any pregnancy in the partner of a male patient, where the male patient was exposed to study drug at the time of conception or conception occurred within two weeks of the last dose of study drug(s).
- Any other relevant safety information including but not limited to reports on drug interaction, overdose, drug abuse or misuse, drug dependency, withdrawal syndrome, medication error, occupational exposure and lack of drug effect (LODE) occurring at any time during the treatment phase;

Any communication concerning safety related information to regulatory authorities or ethics committees including but not limited to:

- Development Safety Update Reports (DSUR) / relevant parts of IND reports for the STUDY;
- Any other safety related reports, issues and queries that are either raised by or communicated to regulatory authorities or ethics committees;

The Investigator/Sponsor may report SAEs using:

A MedWatch 3500A form available at <http://www.fda.gov/medwatch/>

All reports shall be sent to:

[contact]; [contact] and Merck Global Safety. (Attn: Worldwide Product Safety; [contact]).

Facsimile: Bayer:[contact] and Merck [contact]

Address: Global Pharmacovigilance - USA
Mail only Bayer HealthCare
[name]
[name]

Address: [name]
FDX or UPS only [name] for UPS

Reports for all Bayer products can also be phoned in via our Medical Communications Department

[contact]

The Principal Investigator commits to respond promptly to any query from Bayer regarding SAE reports.

Expected adverse events

For this study, the applicable reference document is the most current version of the investigator's brochure (IB) / summary of product characteristics.

Overview listings of frequent events that have occurred so far in the clinical development are shown in the current IB. If relevant new safety information is identified, the information will be integrated into an update of the IB and distributed to all participating sites.

Adverse events of special safety interest

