Bayer: As with any new chemical entity, there is always potential for unexpected adverse events, including hypersensitivity reactions.

Based on data studies with regorafenib and from current knowledge of the pharmacological properties of other small molecule tyrosine kinase inhibitors in this drug class, as soon as there is reasonable suspicion of any of the following AEs, the investigator should immediately notify the sponsor as outlined in Section 7.4.1.4.

Reportable adverse events include:

- Acute renal failure (NCI-CTCAE version 5.0 \geq grade 3) or severe proteinuria (NCI-CTCAE version 5.0 \geq grade 3)
- Interstitial lung disease
- Acute cardiac failure
- Clinically significant bleeding (NCI-CTCAE version 5.0 \geq grade 3)
- Stevens-Johnson Syndrome and erythema multiforme
- Hepatic failure
- Reversible posterior leukoencephalopathy syndrome
- Gastrointestinal perforation or fistula

Merck:

Selected non-serious and serious adverse events are also known as Events of Clinical Interest (ECI) and must be reported within 2 working days to Merck Global Safety. (Attn: Worldwide Product Safety; [contact]).

For the time period beginning when the consent form is signed until treatment allocation, any ECI, or follow up to an ECI, that occurs to any participant must be reported within 2 working days to Merck Global Safety if it causes the participant to be excluded from the trial, or is the

result of a protocol-specified intervention, including but not limited to washout or discontinuation of usual therapy, diet, placebo treatment or a procedure.

For the time period beginning at treatment through 90 days following cessation of treatment, or 30 days following cessation of treatment if the participant initiates new anticancer therapy, whichever is earlier, any ECI, or follow up to an ECI, whether or not related to Merck product, must be reported within 2 working days to Merck Global Safety.

Events of clinical interest for this trial include:

1. an overdose of Merck product that is not associated with clinical symptoms or abnormal laboratory results.
2. an elevated AST or ALT lab value that is greater than or equal to 3X the upper limit of normal and an elevated total bilirubin lab value that is greater than or equal to 2X the upper limit of normal and, at the same time, an alkaline phosphatase lab value that is less than 2X the upper limit of normal, as determined by way of protocol-specified laboratory testing or unscheduled laboratory testing.*

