7.3.2 Pregnancies

The investigator must report to Bayer and Merck any pregnancy occurring in a study subject, or in his partner, during the subject's participation in this study. The report should be submitted within the same timelines as an SAE, although a pregnancy per se is not considered an SAE.

For a study subject, the outcome of the pregnancy should be followed up carefully, and any abnormal outcome of the mother or the child should be reported.

For the pregnancy of a study subject's partner, all efforts should be made to obtain similar information on course and outcome, subject to the partner's consent.

For all reports, the forms provided are to be used.

Progressive disease

If progressive disease leads to signs and symptoms that meet the criteria for an SAE (i.e., hospitalization, disability, death, or important medical event), the signs and symptoms should be reported as an SAE and not the underlying progressive disease.

Death

If any subject dies during the trial or within 30 days of the end-of-treatment visit, the investigator will inform Bayer and Merck and record the cause of death in detail (using the SAE Form) within 24 hours.

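### The dated pregnancy-reporting limits end before the protocol's own 23- and 31-week contraception periods; the gap is small and mainly concerns partners of male patients

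*Combined protocol and SAP*

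**What the plan says.** **Contraception (5.1.1, items 8 and 9; repeated in the synopsis).** Women agree to contraception "for at least 23 weeks after taking the final dose of the investigational drug" and men "for at least 31 weeks after taking the final dose of the investigational drug". The stated basis is five elimination half-lives of the immunotherapy agent, plus 30 days (ovulation cycle) for women or 90 days (spermatogenesis cycle) for men. Neither period is shortened when another anticancer therapy begins.

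**Pregnancy reporting (Assessments and documentation of adverse events).** Pregnancies and breastfeeding exposure are to be reported from treatment allocation "through 120 days following cessation of study treatment, or 30 days following cessation of study treatment if the participant initiates new anticancer therapy". Partners are not mentioned. The comparable window for events of clinical interest (Adverse events of special safety interest) ends "or 30 days following cessation of treatment if the participant initiates new anticancer therapy, whichever is earlier"; the pregnancy bullet has no such tie-break.

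**Expedited reporting (Expedited Reporting of Other Safety Information).** The list covers pregnancies in exposed female patients, with no end date. It also covers partner pregnancies "where the male patient was exposed to study drug at the time of conception or conception occurred within two weeks of the last dose". It is introduced by "awareness of other events such as", so it is illustrative.

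**Other duties.** Reporting of serious adverse events asks for "reports of drug exposure via mother / father with and without adverse events", undated. Section 7.3.2 asks for "any pregnancy occurring in a study subject, or in his partner, during" the subject's participation, a term the protocol does not define. Section 5.2.1 ties pregnancy to the SAE reporting timeline but gives no end date.

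**The concern.** The contraception periods are the protocol's own statement of how long after the last dose a conception should be avoided. Both of the reporting limits given as a number of days or weeks stop earlier. A site that works from those limits could leave unreported a pregnancy conceived while contraception was still required. Whether a broader duty catches it depends on how participation and exposure are read.

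The 30-day limit fits the protocol's reasoning least well, because starting another treatment does not remove antibody already given. At stake is a small part of fetal-safety follow-up. No efficacy, dosing or error-rate question is involved.

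**Working it through.** **Inputs.** Contraception periods of 23 and 31 weeks, with margins of 30 and 90 days (5.1.1, items 8 and 9). Reporting limits of 120 and 30 days (Assessments and documentation of adverse events). Partner limit of two weeks (Expedited Reporting).

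**The plan's own figures.** The half-life h is not given, so 23 and 31 weeks can only be checked for mutual consistency. If both were rounded up to whole weeks from one h:

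- women: 154 < 5h + 30 ≤ 161, so 124 < 5h ≤ 131
- men: 210 < 5h + 90 ≤ 217, so 120 < 5h ≤ 127

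Both hold when 5h is above 124 and at most 127 days, that is, h of about 24.8 to 25.4 days. With h = 25, 155 days rounds up to 23 weeks and 215 days to 31 weeks. The two periods are consistent with each other.

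**Shortfall.** 23 × 7 = 161 days; 31 × 7 = 217 days.

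| | Contraception ends | Less 120 days | Less 30 days |
|---|---|---|---|
| Women | 161 | 41 | 131 |
| Partners, if covered by the bullet | 217 | 97 | 187 |

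For the separate partner limit, 217 − 14 = 203 days.

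**Split between elimination and margin.** Removing the margins leaves 161 − 30 = 131 days for women and 217 − 90 = 127 for men as the implied five half-lives. Beyond day 120 that is 131 − 120 = 11 days and 127 − 120 = 7 days. The remaining 30 of the 41 days and 90 of the 97 are reproductive-cycle margin. With the rounded-up range of 124 to 127 days, the elimination part is about 4 to 7 days for both. Under the 30-day limit it is larger: 131 − 30 = 101 of the 131 days, and 127 − 30 = 97 of the 187.

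**What the other duties catch after the dated limits.**

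- A birth defect is an SAE (7.3.1.2, item e). The documentation section requires any drug-related SAE that comes to the investigator's attention outside the window to be reported, with no end date.
- An uncomplicated pregnancy is not in itself an SAE (7.3.2), so that catch-all does not reach it. The documentation section also says that sites need not actively look for reportable events in former participants.
- Exposed female patients are covered without an end date, and exposure via either parent likewise, but nothing says whether a conception at, for example, day 140 counts as exposure.
- For partners, a separate two-week limb would add little if exposure at conception were already meant to extend to 31 weeks. This suggests that it is not.
- Section 7.3.2 names partners. If participation includes the 24 months of follow-up calls in the section 7 calendar, the shortfall is zero for subjects in follow-up. Section 12 refers to subjects in post-study follow-up as ongoing, which favours that reading, but no text states it.

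**The case against.** The best case against is that these duties are cumulative. The exposure duty under SAE reporting is introduced as additional, and the dedicated pregnancy section names partners. None of the rules forbids later reporting, and a site that follows the broadest one complies with all of them. Most of the 41 and 97 days is precautionary margin. A contraception period prevents and a reporting window monitors, and nothing in the documents says they must be equal. The yield would also be low, since the change adds no active case-finding.

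Much of this stands, and it rules out three stronger readings that a reader might infer:

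- *That pregnancies after day 120 are certain to be lost.* The documents do not show this. Known drug-related birth defects stay reportable at any time, and the exposure and participation duties may catch the rest.
- *That the rules contradict one another and need an order of precedence.* They do not. Cumulative duties need no ranking.
- *That partner reporting stops at two weeks.* It does not. That limb extends an exposure duty inside an illustrative list and is not a cap.

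What does not stand is that the broader duties close the gap. They turn on undefined words, and an uncomplicated late pregnancy falls outside the SAE catch-all. The margin days are still days on which the protocol requires contraception.

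**Conclusion.** The point holds as a minor inconsistency. Against the 120-day limit the shortfall is 41 days for women and, if partners are included, 97 days for partners, of which about 11 and 7 lie within the implied five half-lives. Under the 30-day limit it is 131 and 187 days.

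These figures assume that the window runs on date of conception, which the bullet does not say; if it runs on date of discovery the shortfall is larger. They also take cessation of treatment and final dose as the same day. If the bullet does not cover partners, their two figures fall away and the only dated partner rule is 14 days against 217.

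These are days of window, not missed pregnancies. Few are expected: at most 75 patients (10.1), a median survival of 6.4 months on regorafenib in the historical trial (1.4.2), and mandatory contraception. What may go unreported is mainly a late pregnancy with no known drug-related serious outcome, chiefly in a partner of a male patient.

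**What to change.** - **Assessments and documentation of adverse events:** have pregnancy reporting cover conceptions through at least 23 weeks after the last dose in female subjects and at least 31 weeks in partners of male subjects, whether or not new anticancer therapy starts. Name partners explicitly. Leave breastfeeding-exposure reporting no shorter than it is now.
- **Expedited Reporting of Other Safety Information:** replace two weeks with 31 weeks and keep the limb on exposure at conception.
- **Section 7.3.2:** state that the duty covers at least these periods, including subjects in post-treatment follow-up.
- Leave all other reporting duties in force.

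The cost is protocol wording and a few extra reports. Each brings the outcome follow-up that 7.3.2 already asks for, subject to consent in the case of partners. No visit or test is added, and dosing, DLT rules and the PFS analysis do not change.

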7.3.2 Pregnancies

The investigator must report to Bayer and Merck any pregnancy occurring in a study subject, or in his partner, during the subject's participation in this study. The report should be submitted within the same timelines as an SAE, although a pregnancy per se is not considered an SAE.

For a study subject, the outcome of the pregnancy should be followed up carefully, and any abnormal outcome of the mother or the child should be reported.

For the pregnancy of a study subject's partner, all efforts should be made to obtain similar information on course and outcome, subject to the partner's consent.

For all reports, the forms provided are to be used.

Progressive disease

If progressive disease leads to signs and symptoms that meet the criteria for an SAE (i.e., hospitalization, disability, death, or important medical event), the signs and symptoms should be reported as an SAE and not the underlying progressive disease.

Death

If any subject dies during the trial or within 30 days of the end-of-treatment visit, the investigator will inform Bayer and Merck and record the cause of death in detail (using the SAE Form) within 24 hours.

7.4 Appropriateness of procedures / measurements

The assessments described in the previous sections are widely used and generally recognized as reliable, accurate, and relevant for determining the safety and efficacy of therapies in this

disease.

8. Treatment Evaluation Using RECIST Guideline

Response and progression will be evaluated in this study using the international criteria proposed by the revised Response Evaluation Criteria in Solid Tumors (RECIST) guidelines (version 1.1) (Eisenhauer, et al, 2009). Changes in the largest diameter (unidimensional measurement) of the tumor lesions and the short axis measurements in the case of lymph nodes are used in the RECIST guideline.

8.1 Definitions of Measurable and Non-Measurable Disease

8.1.1 Measurable Disease

A non-nodal lesion is considered measurable if its longest diameter can be accurately measured as ≥ 2.0 cm with chest x-ray, or as ≥ 1.0 cm with CT scan, CT component of a PET/CT, or MRI.

A superficial non-nodal lesion is measurable if its longest diameter is ≥ 1.0 cm in diameter as assessed using calipers (e.g. skin nodules) or imaging. In the case of skin lesions, documentation by color photography, including a ruler to estimate the size of the lesion, is recommended.

A malignant lymph node is considered measurable if its short axis is >1.5 cm when assessed by CT scan (CT scan slice thickness recommended to be no greater than 5 mm).

A lesion in a previously irradiated area is not eligible for measurable disease unless there is objective evidence of progression of the lesion prior to study enrollment. Lesions in previously irradiated areas must be clearly identified as such.

8.1.2 Non-Measurable Disease

All other lesions (or sites of disease) are considered non-measurable disease, including pathological nodes (those with a short axis ≥ 1.0 to <1.5 cm). Bone lesions, leptomeningeal disease, ascites, pleural/pericardial effusions, lymphangitis cutis/pulmonis, inflammatory breast disease, and abdominal masses (not followed by CT or MRI), are considered as non-measurable as well.

Note: ‘Cystic lesions’ thought to represent cystic metastases can be considered as measurable lesions, if they meet the definition of measurability described above. However, if non-cystic lesions are present in the same patient, these are preferred for selection as target lesions. In addition, lymph nodes that have a short axis <1.0 cm are considered non- pathological (i.e., normal) and should not be recorded or followed.

